8.1.3.2 Visit 2b for Patients on Prophylaxis Undergoing PK Evaluation

Four days after first dose the following assessments will be performed and/or recorded in the eCRF

...

- Administration of second dose of N8-GP (*patients must be observed for at least 1 hr after administration for adverse reactions*)

Reminders:

- An appointment for Visit 3, 4 weeks \pm 1 week after *visit 2a* should be made.

8.1.3.3 Visit 7 for Patients on Prophylaxis Undergoing PK Evaluation

...

Blood sampling for local laboratory assessments to be taken within 1 hour prior to dosing:

- Haematology, see section 8.3.6.1
- ~~Urinalysis with sticks provided by the central laboratory, see section 8.3.6.2~~

Blood sampling for central laboratory assessments to be taken within 1 hour prior to dosing:

- Biochemistry, see section 8.3.7.1
- *Coagulation related parameters, aPPT and INR before dosing and 30 min (\pm 10 min) after dosing, see section 8.3.7.2*

...

Reminders:

- An appointment for Visit 8, 36-~~(8 weeks \pm 1~~ *after visit 2a*~~week later~~) should be made.
Withhold N8-GP minimum 96 hours prior to next visit

8.4.1 Follow-up visit (only for patients withdrawn due to development of FVIII inhibitors)

In case of withdrawal due to FVIII inhibitor development, the patient should be scheduled for an EOT Visit as soon as possible and within 1 week after a positive inhibitor test is confirmed via re-testing, preferably prior to initiation of treatment with another FVIII product. One month (4 weeks \pm 2 weeks) after the EOT Visit the patient must attend a FU Visit, please see Section ~~8.3.6~~ 8.3.2.2

8.1.5 Unscheduled Visits

...

- IgE, IgG, HCP see section 8.3.2.3
- N8-GP administration, ~~not for on-demand patients~~

8.2 Efficacy Assessments

...

- *Health Economic questions, see section 8.4.5*

8.2.1 Bleeding Episodes

...

For bleeding episodes the following will be recorded in Patient's eDiary or eCRF:

...

- ~~Haemostatic drug used for~~
- Pain relieving medication
- Dose(s) and Time(s) of administration
- Other therapy used (compression, ice or other)
- Stop of bleed (date and time)
- Categorisation of the bleeding episode (mild/moderate or severe), in the eCRF
- Clinical evaluation of the haemostatic response (excellent, good, moderate or none)
- ~~Bleed related days away from work or school~~

~~Bleed related days using mobility aids~~

8.4.2 Body Measurements

All body measurements (weight, height and BMI) will be performed at Visit 1. On all other visits only weight will be measured. The weight measured at the respective visits should be ~~the weight~~ used for calculating ~~the amount on~~ of N8-GP to be dispensed and the dose of N8-GP to be administered.

- Weight (*registered with one decimal*), wearing light clothing only (kg/pounds) and without shoes
- Height, without shoes (cm/inches), visit 1 only
- BMI calculation (kg/m^2), visit 1 only

8.4.3 eDiaries

eDiaries will be used in this trial. The patient should bring the eDiary to every visit to the site.

The following data will, as a minimum, be captured by the patient or the caregiver in the e-Diary:

- Treatment
- FVIII product used

...

- ~~Bleed related days away from work or school~~
- ~~Bleed related days using mobility aids~~
- *Health Economic questions, see section 8.4.5*

8.4.4.2 ~~Bleeding~~ Haemophilia Treatment History including History of Bleeding Episodes

For patients currently on prophylaxis treatment, the following should be recorded

...

- ~~Number of Bleeding pattern episodes within the last 12 months prior to initiation of prophylaxis therapy was initiated~~

For patients currently on on-demand treatment the following should be recorded

Number of months on on-demand

12 Adverse Events and Pregnancies

12.1 Definitions

...

b) The term “hospitalisation” ~~describes a period of at least 24 hours. Over night stay for observation, treatment at emergency room or treatment on an out subject basis does not constitute a hospitalisation. However, medical judgement must always be exercised and when in doubt the case should be considered serious.~~

~~Hospitalisations for administrative, trial related and social purposes do not constitute hospitalisations as defined by the seriousness criteria, and should therefore not be reported as such. Likewise, hospital admissions for surgical procedures planned prior to trial inclusion are not considered AEs. is used when a subject is:~~

- *Admitted to a hospital/in-subject (irrespective of the duration of physical stay), or*
- *Not admitted to a hospital/not in-subject, but stays at the hospital for treatment or observation for more than 24 hrs.*

Medical judgement must always be exercised, and when in doubt, the hospital contact should be regarded as a hospitalisation. Hospitalisations for administrative, trial related and social purposes do not constitute AEs and should therefore neither be reported as AEs or SAEs. Likewise, hospital admissions for surgical procedures planned prior to trial inclusion are not considered AEs or SAEs.

19 Ethics

...

19.1 Informed Consent Form for Trial Patients

...

A voluntary, signed and personally dated, ~~including time~~, informed consent form will be obtained from the patient prior to any trial-related activity.

The responsibility for seeking informed consent must remain with the Investigator or an adequately medically qualified person delegated by the Investigator. The written informed consent must be signed and personally dated, ~~including time~~, by the person who seeks the informed consent.

22 Critical Documents

Substantial Protocol Amendment
Trial ID: NN7088-3859
UTN: U1111-1119-7416
EudraCT No.: 2011-001142-15

~~CONFIDENTIAL~~

Date:	09 December 2011	Novo Nordisk
Version:	1.0	
Status:	Final	
Page:	15 of 18	

...

For US sites:

~~Signed and dated FDA form 1572 must be completed and signed for by each US Investigator (and individual US clinical trial staff if directly involved in the treatment or evaluation of research making a direct and significant contribution to the data).~~

24 Reports and Publications

...

Attachment II – Spain List of Key Staff and Relevant Departments

~~Investigator:~~ Name:
*National Coordinating
Investigator:*

Investigator: Name:

Title:

Address:

Tel:

Local laboratory(ies): Name:

Address:

Tel:

Substantial Protocol Amendment
Trial ID: NN7088-3859
UTN: U1111-1119-7416
EudraCT No.: 2011-001142-15

~~CONFIDENTIAL~~

Date: 3 February 2012
Version: 1.0
Status: Final
Page: 1 of 4

Novo Nordisk

Substantial Protocol Amendment-Local France

N° 5-FR

to Protocol, Final version 1.0, dated 30-Sep-2011, and Global substantial amendment N°2, dated 9-Dec-2011

Trial ID: NN7088-3859

pathfinder™ 2

**A Multi-national Trial Evaluating Safety and Efficacy,
including Pharmacokinetics, of NNC 0129-0000-1003
when Administered for Treatment and Prophylaxis of
Bleeding in Patients with Haemophilia A**

Trial phase: 3

Applicable to France

Amendment originator:

~~This confidential document is the property of Novo Nordisk. No unpublished information contained herein may be disclosed without prior written approval from Novo Nordisk. Access to this document must be restricted to relevant parties.~~

Substantial Protocol Amendment
Trial ID: NN7088-3859
UTN: U1111-1119-7416
EudraCT No.: 2011-001142-15

~~CONFIDENTIAL~~

Date:	3 February 2012	Novo Nordisk
Version:	1.0	
Status:	Final	
Page:	2 of 4	

Table of Contents

	Page
Table of Contents.....	2
1 Introduction including rationale for the substantial protocol amendment	3
2 Changes to Protocol	4

1 Introduction including rationale for the substantial protocol amendment

This local substantial amendment is being issued following Ethics Committee decision: due to absence of data from clinical trials in adult population, patients below 18 years of age cannot be included in this trial.

The following change has been made to the protocol:

- Inclusion criterion N° 4 has been modified to exclude patients of age < 18 years in France.

Any new text in this amendment is written in "*Italic*". Any text deleted from the protocol is written with a ~~strike through~~.

2 Changes to Protocol

1 Summary

Key Inclusion Criteria

- Age >12 years and body weight ≥ 35 kg (except for Croatia ~~and~~, The Netherlands *and France* where the lower age limit will be 18 years)

6 Trial Population

6.2 Inclusion Criteria

...

4. Age ≥ 12 years and body weight ≥ 35 kg (except for Croatia, ~~and~~ The Netherlands *and France* where the lower age limit will be 18 years)

Substantial Protocol Amendment

no 6

to Final Protocol, version 2, dated 09 December 2011

Trial ID: NN7088-3859

pathfinder™ 2

**A Multi-national Trial Evaluating Safety and Efficacy,
including Pharmacokinetics, of NNC 0129-0000-1003
when Administered for Treatment and Prophylaxis of
Bleeding in Patients with Haemophilia A**

Trial phase: 3

Applicable to all countries

Amendment originator:

This ~~confidential~~ document is the property of Novo Nordisk. ~~No unpublished information contained herein may be disclosed without prior written approval from Novo Nordisk. Access to this document must be restricted to relevant parties.~~

Table of Contents

	Page
Table of Contents	2
1 Introduction including rationale for the substantial protocol amendment	3
2 Changes to Protocol	5
2.1 List of Abbreviations	5
2.2 Section 1 Summary	5
2.3 Section 2	5
2.4 Section 5 Trial design	5
2.5 Section 6 Trial Population	7
2.6 Section 8 Methods and Assessments	7
2.7 Section 11 Concomitant Illness and Concomitant Medication	11
2.8 Section 12 Adverse Events and Pregnancies	11
2.9 Section 18 Statistical Considerations	13
3 Changes to Sample Subject Information Informed Consent Form	19

1 Introduction including rationale for the substantial protocol amendment

This global substantial protocol amendment is being issued primarily as a response to a Special Protocol Assessment (SPA) request sent to the US FDA in connection with submission of the NN7088-3859 protocol in the United States and includes the following:

Section 18:

- Annualised bleeding rate in prophylaxis arm. The calculation of annualised bleeding rate for withdrawals has been changed. Imputation will also be performed for withdrawals within the first month. An annualised bleeding rate of 24 will be used for imputation for all patients withdrawing in the first month, including those with zero bleeds
- Sample size calculations have been changed. For the inhibitor test a true inhibitor rate of 0.5% instead of 1% is now assumed. This is based on the experience with clinical trials with turoctocog alfa. For the prophylaxis test, the impact on the power of the change in imputation rule for early withdrawals without bleeding episodes is accounted for
- An interim analysis has been added in order to evaluate the over-dispersion (only) once approximately 90 patients have entered into the prophylaxis arm. If the estimated over-dispersion is greater than 6 then the planned sample size will be adjusted up to include 160 prophylaxis patients instead of 120 patients. The planned sample size will not be increased without issuing a further amendment
- Additional sensitivity analyses have been added both for haemostatic response and for annualised bleeding rate
- Other editorial adjustments have been made to the statistical section of the protocol (section 18) to better align with the wording of the protocol endpoints in section 4 of the protocol.

In connection with this protocol amendment other clarifications to the protocol have been made:

- Sections 1 and 6: France has been added to the list of countries that will not allow adolescents to participate in the trial
- Section 1: Clarification of the definition Exposure Days (ED) has been added
- Sections 5, 6 and 11: Changes to these sections have been made in order to allow patients to use their current FVIII product in case they need to treat a bleeding episode immediately at home in the period between the first two doses of N8-GP (visit 2a and visit 2b). The changes have been made in consideration of patients' safety
- Sections 5: The conditions for starting up pathfinder^{TM3} (NN7088-3860) has been aligned with the conditions stated in the pathfinder^{TM3} protocol
- Sections 5 and 8: Symptoms that can relate to stop of a bleeding episode have been added. This in order to guide investigators and patients on how to determine the stop time of a bleeding episode

- Sections 5 and 6: Guidance for rescheduling of PK sessions in case of a bleeding episode during a PK sampling session has been added
- Section 5: Requirement for documentation of investigators review of the patient's eDiary at every visit has been added
- Section 8: text regarding Documentation of Inhibitor Status clarified
- Section 8: Clarifications have been made to the viral assessments.
- Section 8: Recording the urine analysis results has been changed from recording the results directly into the eCRF to recording this on the laboratory requisition form. This has been changed to reflect the current trial set up
- Section 8: Time point for genotype testing has been corrected from visit 1 to visit 3 in order to align with the rest of the protocol
- Section 8: The first two doses of N8-GP administrated at the hospital will be documented in the e-CRF and *not* in the eDiary. This has been changed due to the current set up of the trial
- Sections 8 and 12: Reporting of a MESI in case of *one* positive inhibitor test has been clarified
- Section 12: Some text has been amended to make the text more clear
- Other editorial corrections have been made to the protocol
- Attachment I to the protocol has been updated due to changes in key personnel

The following changes have been made to the Subject Information/Informed Consent Form and are therefore reflected in this global substantial amendment:

- Section 1.3: guidance on treatment of a bleeding episode between visit 2a and 2b
- Section 3.2: update to the identification of lab samples

In this substantial protocol amendment:

- Any new text is written *in italics*.
- Any text deleted from the protocol is written using ~~strike through~~
- Minor typographical changes not affecting the content of the text, e.g. grammatical and spelling errors will not be disclosed in the following sections

The protocol version 4 incorporates all the above changes.

2 Changes to Protocol

2.1 List of Abbreviations

pd-aPCC plasma derived activated plasma ~~prothrombin complex coagulation factor concentrates~~

pd-PCC plasma derived ~~prothrombin complex plasma coagulation factor concentrates~~

2.2 Section 1 Summary

Trial Population:

Foot note added: *An “exposure day” is defined as any day the patient has been exposed to N8-GP including on demand, prophylaxis, during surgery and in PK sessions. If N8-GP is administered more than once during the same day, this will still count as one exposure day*

Key Inclusion criteria:

Age ≥ 12 years and body weight ≥ 35 kg (except for Croatia, ~~and~~ The Netherlands *and France* where the lower age limit will be 18 years)

2.3 Section 2

Table 2–1 Flow Chart for Patients on Prophylaxis and On-Demand Treatment

‘X’ has been added to the follow-up visit in the flowchart to indicate that N8-GP binding antibodies must be measured.

2.4 Section 5 Trial design

5.1 Type of Trial:

...

Furthermore, if the patients need to undergo surgery during the present trial they can switch into the surgery trial pathfinderTM 3 and upon completion of the surgery they can return to the pathfinderTM 2^d trial. Recruitment into the surgery trial pathfinderTM 3 will begin after successful treatment of bleeding episodes with N8-GP in at least 5 patients in the pivotal trial pathfinderTM 2. ~~For US:~~ The surgery trial will not be initiated until at least 20 bleeding episodes in at least 10 patients are treated with N8-GP *in the present trial*.

5.3 Treatment of Patients

...

The following medications are not allowed during the course of the trial until after the EOT visit:

- Bypassing products: rFVIIa, pd-PCC and pd-aPCC
- Coagulation factors containing products ~~FVIII~~, FIX, FVII and FVIII other than N8-GP
(exception: current FVIII is allowed until 72 hours before visit 2a and in case of home treatment of a bleeding episode that requires immediate treatment between visit 2a and 2b)

5.3.2 Treatment of Bleeding Episodes

...

Any dose used for treatment of a known active bleed must be recorded as treatment of bleed and not as prophylaxis treatment. When the bleed has resolved (*e.g. pain reduction and no increase in swelling*), the patient can resume the prophylaxis treatment.

If a dose for treatment of a bleed is taken, the next prophylaxis dose should follow the original dosing scheme and not be altered by the additional treatment of bleed administration. If a bleed occurs on the same day as the planned prophylaxis, the dose must be registered for the bleed and not as prophylaxis.

If a bleeding episode occurs between visit 2a and 2b, the patient must contact the site and preferably come to the site for treatment with N8-GP. In case of a bleeding episode between visit 2a and 2b that requires immediate treatment or the Investigator judges it as necessary, the patient can treat the bleed at home with his previous FVIII product..

If a haemostatic response cannot be achieved after 48 hours using adequate doses of N8-GP treatment when treating bleeding episodes, another FVIII product may be selected at the discretion of the Investigator. The use of other FVIII products will result in withdrawal of the patient (*exception: current FVIII product is allowed until 72 hours before visit 2a and in case of home treatment of a bleeding episode that requires immediate treatment between visit 2a and 2b*).

An electronic diary (eDiary) will be kept to register all bleeding episodes and their treatment (*except treatment with the patients' current FVIII product between visit 2a and 2b in case of a bleeding episode that requires immediate treatment at home. In this case the information will be entered into the eCRF*). The Investigator must review the eDiary data and rate the bleeding episodes at every visit. *The review of the eDiary must be documented.*

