6.5 Withdrawal Criteria

The patient may withdraw at will at any time.

The patient may be withdrawn from the trial at the discretion of the Investigator due to a safety concern or if judged non-compliant with trial procedures.

A patient must be withdrawn if the following applies:

1. Haemostasis not achievable with N8-GP: The bleed cannot be controlled after 48 hours using adequate doses of N8-GP
2. FVIII inhibitor (≥ 0.6 BU/mL) as confirmed by re-testing by Central Laboratory
3. Allergy/anaphylaxis to the trial product
4. Use of Coagulation Factors: FVIII, FIX and FVII-containing products other than N8-GP and other FVIII-containing products like fresh frozen plasma or cryoprecipitate. (**Exception:** current FVIII allowed until 72 hours before Visit 2a)
5. Incapacity or unwillingness to follow the trial procedures

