2.5 Section 6 Trial Population

6.2 Inclusion criteria:

Age ≥ 12 years and body weight ≥ 35 kg (except for Croatia, ~~and~~ The Netherlands *and France* where the lower age limit will be 18 years)

6.4 Criteria for rescheduling planned visits:

Criteria 3: In a bleeding state (all visits including PK). *If a patient experiences a bleeding episode during a PK session between visit 2a and 2b, PK sampling will be stopped and the patient will receive treatment with N8-GP, (or the patients' previous FVIII product if the bleeding episode occurs at home and requires immediate treatment)^g. In case of mild or moderate bleeding episodes, rescheduling of PK sessions can be done at the discretion of the Investigator taking the patient's safety into account. In case of a severe bleeding episode the PK session must be discontinued.*

Footnote g: A 7 days wash-out is needed before the rescheduled PK session if the bleeding episode was treated with N8-GP and a 4 days wash-out is needed if the bleeding episode was treated with previous FVIII product.

6.5 Withdrawal Criteria:

- Criteria 4: Use of Coagulation Factors FVIII, FIX and FVII-containing products other than N8-GP and other FVIII-containing products like fresh frozen plasma or cryoprecipitate (**Exception:** current FVIII is allowed until 72 hours before visit 2a *and in case of home treatment of a bleeding episode that requires immediate treatment between visit 2a and 2b*)

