2.6 Section 8 Methods and Assessments

8.1.2 Visit Schedule for Patients on Prophylaxis not Undergoing PK Evaluation and for Patients on On-Demand Treatment

At visit 2a, the patients will have their first dose of N8-GP (50 U/kg ~~BW~~) administered at the site. The second dose (50 U/kg BW) is given at visit 2b 4 days after visit 2a. If a bleeding occurs during this period the patient must *contact the site and preferably* come to the site for treatment with N8-GP. *If the patient has a bleeding episode that requires immediate treatment or the Investigator judges it as necessary, the patient can treat himself at home with his previous FVIII product.*

After each of the 2 initial doses of N8-GP, patients must be observed for adverse reactions for at least 1hr after dosing.

The samples taken post-dose must not be taken from the same vein as previously used for administration of N8-GP.

Patients will be provided with an eDiary and will be carefully trained in the use of this eDiary including instructions in reporting details of bleeding episodes and prophylactic treatment including doses administered at *all visits after visit 2b*.

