For patients who were withdrawn in the Pivotal part the planned exposure time will be until the end of the pivotal part as described above. For patients who were withdrawn in the main part after the pivotal part ended, the maximum expected exposure time will be used, i.e. 100 weeks as this is the maximum duration for main phase. For patients withdrawn during extension phase part 1, the planned exposure is 24 weeks (duration of extension phase part 1) added to the actual exposure in main

For calculations only including the randomised period, the planned exposure time will be the time from visit 14 to visit 17, i.e. 24 weeks. Patients that change from Q7D to non-randomised part of Q4D will have their bleeds imputed using a planned exposure time of 24 weeks using the same approach as in the pivotal part of the trial even though they are not withdrawn from the study. This is to avoid bias for randomized Q7D caused by patients withdrawing due to high bleeding rate.

Calculations of ABR for extension phase part 2:

For patients withdrawn prior to extension phase part 2, planned exposure is calculated as explained above. For patients withdrawing during extension phase part 2, planned exposure in extension phase part 2 will be calculated using the overall cut-date (15Aug2017) as planned end date. The actual exposure time in main and extension phase part 1 is added to the planned exposure time in extension phase part 2, to get the overall planned exposure time for a withdrawn patient.

Planned exposure time is only relevant for the treatment regimen the patient is on, when being withdrawn. Time on other regimens and time in surgery trial is subtracted when calculating planned exposure time.

For patients who withdrew within 1 month, imputation will be conducted by assuming an annualised bleeding rate of 24 (bleeds per year) for the missing period. This also applies to change from Q7D to Q4D in the randomised part of extension phase part 1.

Estimates of the annualised bleeding rates for each regimen will be provided together with the 95% confidence intervals as described in the protocol.

Sensitivity analyses:

Analysis applying a different model

A sensitivity analysis based on a negative binomial regression model with number of bleeding episodes requiring treatment as the outcome variable, and adjusting for exposure time will be performed.

Analysis without imputation to planned trial duration

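### Between Visits 2a and 2b the protocol permits previous FVIII at home on two triggers, but the withdrawal exception covers only one of them

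*Protocol*

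**What the plan says.** All the relevant text comes from Protocol Amendment 6, and no later amendment in the documents aligns it.

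**Permission.** Section 5.3.2 asks the patient to contact the site and preferably be treated there with N8-GP. It then allows an alternative: if the bleed "requires immediate treatment or the Investigator judges it as necessary, the patient can treat the bleed at home with his previous FVIII product". Section 8.1.2, which covers on-demand patients and prophylaxis patients without PK sampling, repeats this: "requires immediate treatment or the Investigator judges it as necessary, the patient can treat himself at home with his previous FVIII product". Section 8.1.3.1 says the same for PK patients. Each of the three has two triggers joined by an or.

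**Ban and withdrawal.** Section 6.5 opens its list with "A patient must be withdrawn if the following applies". Criterion 4 is use of other FVIII products, and between these visits it exempts such use only "in case of home treatment of a bleeding episode that requires immediate treatment between visit 2a and 2b". Section 5.3.2 states the consequence as well: "The use of other FVIII products will result in withdrawal of the patient", with the same one-trigger exception. Sections 5.3, 8.2.1 and 11 carry that exception too.

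**Neighbouring rules.** The PK rescheduling rule in 6.4 allows previous FVIII only for a bleed at home with immediate need. In 5.3.2, the exception that moves recording from the eDiary to the eCRF is limited in the same way. Section 8.4.3 sends any use of previous FVIII between the two visits to the eCRF, with no such limit.

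**Analysis.** For a prophylaxis patient who withdrew within one month, SAP 2.2.2 says "imputation will be conducted by assuming an annualised bleeding rate of 24 (bleeds per year) for the missing period".

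**The concern.** The permission is wider than the exemption. A site that follows 5.3.2 can send a patient home to treat a bleed with his previous product on the Investigator's judgement. A site that then applies 6.5 must withdraw him for it. Two sites could therefore handle the same event differently, and section 5.3.2 disagrees with itself within a few paragraphs.

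Withdrawal at this point has several consequences:

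- Exclusion criterion 2 (section 6.3) bars a patient withdrawn after receiving N8-GP from re-entering.
- With fewer than 50 exposure days and no inhibitor, he does not count in the denominator of the inhibitor co-primary endpoint (Protocol 18.2.2, SAP 2.2.2).
- In the prophylaxis arm, he enters the annualised bleeding rate (ABR) co-primary analysis at 24 bleeds per year for almost all of his planned time. The cause would be a conflict of wording and not how he bled.

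**Working it through.** **1. The passages compared**

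- *Immediate need or Investigator judgement:* 5.3.2 (permission), 8.1.2, 8.1.3.1.
- *Immediate need only:* 5.3, 5.3.2 (withdrawal exception), 6.5 criterion 4, 8.2.1, 11, 6.4 (PK rule), 5.3.2 (recording exception).
- *No trigger stated:* 8.4.3 (recording in the eCRF).

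The only patients caught are those treated at home on the second trigger without the first. Later amendments to 6.5 change the inhibitor criteria and, in No. 2, add anticoagulants (that one precedes No. 6). None shows a change to criterion 4 that widens the exception.

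**2. Bleeds imputed for one such patient**

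Inputs: 24 bleeds per year, withdrawal at about day 4 (Visit 2b), and planned durations of 7, 12 and 19 months (Protocol 18.1).

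- 12 months: 24 × (365.25 − 4)/365.25 = 23.7 bleeds
- 7 months: 24 × (7/12 − 4/365.25) = 13.7 bleeds
- 19 months: 24 × (19/12 − 4/365.25) = 37.7 bleeds

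**3. The plan's power, reproduced**

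Inputs (Protocol 18.1 as amended by No. 6, and 18.2.1): threshold 8.5, over-dispersion 5, 120 prophylaxis patients, one-sided 2.5% level. The true rate of 6.8 is raised to 7.0 by one first-month withdrawal (24/120 = 0.2).

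Power = Φ((8.5 − r)/√(5r/120) − 1.96)

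At r = 7.0 this is Φ(1.5/0.540 − 1.96) = 79.3%, against a stated 79%. The other rows of the table also reproduce: 89.1% (stated 89%), 97.0% (97%), 87.4% (87%) and 71.8% (72%).

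**4. One more first-month withdrawal, as illustration**

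- *Plan's own step, +24/120 per patient.* With two withdrawals r = 6.8 + 2 × 0.2 = 7.2, and power = Φ(1.3/0.548 − 1.96) = 66.0%.
- *Replacement throughout.* The imputed 24 takes the place of the patient's 6.8, so each adds 17.2/120 = 0.143. With one withdrawal r = 6.943 and power is 82.5%. With two, r = 7.087 and power = Φ(1.413/0.543 − 1.96) = 73.9%.

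The two conventions start from different baselines (79.3% and 82.5%), so each result should be read against its own. One extra patient is an assumption.

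**The case against.** The strongest reply is that this is a drafting gap with almost nobody in it. Section 5.3.2 already requires a bleed that needs factor to be treated once it is recognised, so most such bleeds would count as immediate need. Investigator judgement can be read as a judgement that immediate treatment is necessary. The rationale in the introduction to Amendment 6 mentions only patients using their current product "in case they need to treat a bleeding episode immediately at home in the period between the first two doses of N8-GP". Section 8.4.3 records any use of previous FVIII in this window without mentioning withdrawal. All this makes a deliberate withdrawal rule unlikely and the affected group probably small. It does not remove the conflict: the or appears in all three permissions, the withdrawal rule is mandatory, and nothing tells a site which passage prevails.

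Existing provisions also limit the damage. Section 6.6 allows replacement of withdrawn patients until about 105 (or 145) prophylaxis patients have had 50 exposure days. Sensitivity analyses without any imputation, and without the 24-per-year rule for first-month withdrawals, are specified in Protocol 18.2.2 and SAP 2.2.2. They would expose a distortion but do not change the primary test. The SAP is dated January 2019 and says the pivotal part has been reported, so it cannot change how those events were handled.

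A reader might infer more than the text supports:

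- *That anyone using previous FVIII as permitted must be withdrawn.* Patients with immediate need are expressly exempt.
- *That everyone who bleeds in the window is affected.* At 6.8 bleeds per year, 1 − exp(−6.8 × 4/365.25) = 7.2% of patients, or about 9 of 120, would have a bleed in four days. That counts all bleeds, not those treated at home on judgement alone.
- *That the imputation covers every patient and the whole planned period.* It covers the missing period only, and only in the prophylaxis analysis. On-demand patients follow the same visit rule but are outside that endpoint.

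**Conclusion.** The inconsistency is real and unresolved in the documents. Read literally, a mandatory withdrawal rule catches conduct that another section permits, but only for home treatment on Investigator judgement without immediate need.

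The documents do not give the number of patients affected, and it may be very small or zero. The drop in power to about 66% or 74% shows how sensitive the ABR test is to one extra first-month withdrawal. It is not a forecast. It rests on the plan's normal approximation, over-dispersion 5, 120 patients and one extra case. The effect on the inhibitor denominator is likewise limited by replacement.

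This is a consistency defect that is cheap to correct. It is not evidence that the co-primary results are biased.

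**What to change.** Reconcile the passages so that one trigger applies throughout: the permission (5.3.2, 8.1.2, 8.1.3.1), the prohibited-medication and withdrawal exceptions (5.3, 5.3.2, 6.5 criterion 4, 8.2.1, 11), the PK rule in 6.4, and the recording rules in 5.3.2 and 8.4.3. Which trigger to use is a clinical decision for the sponsor, and this review takes no position on it.

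No separate SAP rule is needed. The 24-per-year imputation applies to patients who withdrew, and use that the reconciled protocol permits would not be a withdrawal.

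The cost is one clause, repeated in the listed sections, in a protocol amendment. No design, sample-size or analysis change follows, and the planned power stays at 79%.
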